5.10 Data Management

Data will be stored on electronic CRFs using an Electronic Data Capture system, and exported to an analysis tool (Excel by Microsoft and/or MATLAB by Mathworks Inc.).

No subject-identifiable information will be transferred. Instead, study data pertaining to a particular subject will be entered using a de-identified alphanumeric subject code. This is described further in section 5.8.7.

Analysis data will be backed-up in accordance with Exact Imaging's standard operating procedures.

5.10.1 *Data review*****

Source data will be verified by the Study Monitor, as described in section 5.8.5.1.

5.10.2 *Data verification and validation*****

Source data will be recorded in the Electronic Data Base and/or on case report forms (CRFs) as described in section 5.8.6.

Source data will be verified by the Study Monitor, as described in section 5.8.5.1.

This data will be collected by the Study Coordinator or Study Monitor (collect de-identified films), and forwarded to Exact Imaging personnel for analysis. The accuracy of the data will be verified by Exact Imaging by manual comparisons between:

- data on CRFs and on images stored on ExactVu

5.10.3 *Data retention*****

All documents related to this investigation will be handled in accordance with Exact Imaging's quality system procedure *QSP 4.2.3 Control of Documents*. This procedure describes the way Exact Imaging controls its documents in a way that involves a formal document review, approval and release process, and prevents outdated or obsolete documents from being used. This procedure is designed to comply with the requirements of ISO 13485.

Exact Imaging, and each Site Principal Investigator shall maintain the records collected during the investigation for a period of 2 years after the latter of the following two dates: the date on which the investigation is terminated or completed, or the date that the records are no longer required

for purposes of supporting a premarket approval application. Institutions will retain data collected according to local institutional or applicable requirements of the Ethics Board/IRB.

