5.8.1.3 Endpoints

Primary endpoint

Number of men diagnosed with csPCa based on the pathology samples collected during the biopsy procedure through:

- MicroUS samples (targeted and systematic samples taken under microUS imaging only without mpMRI)
- mpMRI/US Fusion samples (targeted and systematic samples taken under conventional ultrasound imaging with mpMRI targets)

Secondary endpoints

As above, with the addition of combined results for men undergoing Fusion biopsy on the microUS system:

- mpMRI/MicroUS samples (targeted and systematic samples taken under microUS imaging with mpMRI)

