5.8.5.1 Site Visits

Further to Exact Imaging's role for the investigation, Exact Imaging will provide support to ensure the quality of data related to the investigation by:

- on-site visits to each site at the beginning and end of the study, and as required to ensure optimal image quality and assist with protocol training
- thorough review of CRF data to identify and follow-up on missing data, inconsistent data, data outliers, and potential CIP deviations that may be indicative of systemic or significant errors in data collection and reporting and as determined by the study sponsor

An on-site visit at the beginning of the investigation will include the following activities:

1. Review of supplies required for the investigation
 - a. Check that there continues to be an adequate supply of sterile transducer sheaths and needle guides
2. Review of device maintenance and image quality assessment to ensure devices are functioning correctly
3. Review issues with investigators
 - a. Discuss and investigate any performance issues and device deficiencies and resolved as required. These issues will be documented according to Exact Imaging service procedures including details about steps taken to resolve issues
 - b. Review any changes to the investigative team and update details in the CIP as required
 - c. Provide training where changes to the investigative team requires it

Any on-site visits during the investigation will include the following activities:

1. Review subject enrolment
2. Review study data
 - a. Review data collected on CRF
 - b. Check CRF for completeness and accuracy. Ensure CRFs are filled out properly
 - c. Check ExactVu for images. There must be at least one image saved on the system to correspond to each subject.
 - d. Verify data. Compare images stored on ultrasound system with CRF data and pathology report
3. Copy and collect image data
4. Copy and collect completed CRFs

Along with providing assurance of the quality of investigational data, these actions will allow Exact Imaging to assess compliance with the CIP and required procedures. Exact Imaging staff will make all documentation and reports from these visits available to the site Study Monitor for inclusion in study records as required.

For cases in which Exact Imaging personnel observe biopsy procedures during a site visit, they shall neither perform medical procedures nor contact the study subject, but will provide support through instruction where required.

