5.9.7 Procedures for reporting deviation from the statistical plan

Where the analysis of case data does not handle unexpected data, Exact Imaging in conjunction with the Principal Investigators and 3rd party biostatistician will establish a strategy to modify the analysis algorithm and apply it to all data. Such modifications will include validation of the algorithm prior to its acceptance for use.

These modifications will be updated and described in the CIP, and/or as in the final report (as appropriate) along with justification for them.

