5.9.10 Treatment of missing, unused data

If a study subject withdraws from the main trial prior to imaging, his consent form will be retained, and the reason for exclusion of the data will be handwritten on the form as "withdrawn prior to imaging". Similarly, if a study subject withdraws from the main trial following his imaging, his consent form and CRF will be retained, and both will be marked "withdrawn following imaging".

This will allow data to be collected about the number of patients that withdrew from the investigation prior to the imaging procedure, and the number that withdrew after the procedure.

The same process will be applied to any circumstance of incomplete or incorrect data, with an indicator handwritten on his consent form and CRF to provide information about why the record is not used for analysis.

5.9.11 *Exclusion of data*****

Conditions that would result in the exclusion of data would be if any data verification activity showed that data was recorded on the CRF incorrectly, or if the pathology report showed any inconsistency with information on the CRF.

If such incorrect data was discovered, data for this subject will not be included in any analysis, and the CRF for the subject will be marked to indicate that the data is excluded.

5.9.12 *Subjects at multi-center investigations*****

This information is provided in section 5.8.3.7.

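### Section 5.9.11 excludes men with record errors instead of correcting the record, and one listed check uses ExactVu images that the MRI/US arm lacks by design, so exclusions may differ by arm

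*Combined protocol and SAP*

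**What the plan says.** Four parts of the combined protocol and SAP bear on this point.

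- **Exclusion rule (5.9.11).** A subject's data are excluded "if any data verification activity showed that data was recorded on the CRF incorrectly, or if the pathology report showed any inconsistency with information" entered in the case report form. The exclusion covers all analyses. The rule is not limited to any arm and offers no route by which a corrected record stays in.
- **Manufacturer's check (5.10.2).** The data are "forwarded to Exact Imaging personnel for analysis. The accuracy of the data will be verified by Exact Imaging by manual comparisons between" two sources: CRF entries and the images held on ExactVu. No other comparison is listed for this check.
- **Platform by arm (5.8.1.3).** The comparator's endpoint comes from "targeted and systematic samples taken under conventional ultrasound imaging with mpMRI targets". ExactVu is the imaging system of the MicroUS and MRI/MicroUS arms.
- **Other verification.** Section 5.10 has the Study Monitor verify source data. Section 5.8.5.1 gives the manufacturer a review of CRF data and a site-visit item: "Compare images stored on ultrasound system with CRF data and pathology report". Section 5.8.6 adds logic checks. None of these is limited by arm.

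For unexpected data, 5.9.7 says that the manufacturer, the Principal Investigators and a third-party biostatistician "will establish a strategy to modify the analysis algorithm and apply it to all data". The change may be described in the CIP or in the final report.

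The only masking described is in 5.4.6, where the biopsy operator in the MRI/MicroUS arm does not see the MRI until unblinding.

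**The concern.** A data-entry error can normally be put right against source. Removing the man instead is an avoidable post-randomisation exclusion, and it breaks the comparison that randomisation set up.

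Three features make this more than lost sample size. First, one listed check has material to work on only in the microUS-based arms, so it can produce exclusions on one side only. Second, the primary endpoint is read from pathology, and a pathology/CRF mismatch is itself a reason for exclusion, so an exclusion may be decided with the outcome in view. Third, nothing says that the people deciding are masked to arm or result.

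In a non-inferiority trial, losing csPCa-negative men from the microUS side raises its detection rate and favours a positive conclusion. Losing csPCa-positive men does the opposite and could sink a trial that should succeed.

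**Working it through.** **Inputs from the plan.** 43% csPCa detection in each group, 10-point margin, 90% power, 1082 subjects (5.9.3). Planned groups: 600 MRI/US against 200 + 400 = 600 microUS-based (5.9.1, 5.9.2). Interim at 50% recruitment with p < 0.0026, final 0.024 (section 5.9.6, termination criteria).

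**Reproducing the plan's figures.** At one-sided 0.024:

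n = 2 × 0.43 × 0.57 × (1.977 + 1.282)² / 0.10² = 520.6 per group.

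With the usual continuity correction, n/4 × [1 + √(1 + 4/(0.10n))]² = 540.4, rounded up to 541, and 2 × 541 = 1082. A two-look O'Brien-Fleming boundary at half the information has critical values 2.797 and 1.977, that is one-sided p of 0.0026 and 0.0240. The plan's figures are reproduced and none is disputed here.

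**Effect of one-sided exclusion.** The plan gives no exclusion rate, so the fraction e of the 600 microUS-based men removed is an assumption (1%, 2%, 3%, 5%). After exclusion that group has 600(1 − e) men, and its expected rate is:

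- only csPCa-negative men removed: p/(1 − e)
- only csPCa-positive men removed: (p − e)/(1 − e)
- outcome-neutral removal: p, unchanged

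The standardised distance from the margin is D = (p_micro − 0.43 + 0.10)/SE, with SE from the unpooled variances. The chance of declaring non-inferiority is 1 − P(Z₁ < 2.797 and Z₂ < 1.977), where Z₁ and Z₂ have means D√0.5 and D and correlation √0.5. This assumes that exclusions occur at the same rate before and after the interim.

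One line in full, e = 2%, true rate 33%, negatives only: 12 men removed, 588 left; 0.33/0.98 = 33.67%; SE = √(0.43 × 0.57/600 + 0.3367 × 0.6633/588) = 0.0281; D = 0.0067/0.0281 = 0.24; false non-inferiority 4.3%.

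| e (men) | False non-inferiority, 33% v 43%, only negatives removed | Power, 43% v 43%, only positives removed |
|---|---|---|
| 0 | 2.5% | 94% |
| 1% (6) | 3.3% | 91% |
| 2% (12) | 4.3% | 87% |
| 3% (18) | 5.5% | 82% |
| 5% (30) | 8.8% | 68% |

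Counting the final look alone gives slightly lower false-positive figures: 2.4% rising to 3.2%, 4.1%, 5.3% and 8.6%.

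If exclusion is unrelated to outcome, type I error does not move, and at e = 5% power falls by less than one percentage point (93.6% to 93.0% on the final look).

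**The case against.** The strongest reply is that the plan's verification is wider than 5.10.2. Study Monitor verification, CRF review, logic checks and the pathology/CRF comparison all apply without limit by arm, and each could exclude an MRI/US man. This stands. A reader might infer that verification exclusions can fall only on the microUS arms; the documents do not support that. The asymmetry belongs to the ExactVu-image check alone.

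Even that asymmetry is by design rather than certain. Section 5.8.5.1 asks for a saved image for each subject in an item about ExactVu, 5.8.7 has the subject identifier recorded on ExactVu, and the sweep in 5.4.6 carries no arm restriction. Read literally, these would flag MRI/US men rather than spare them. That is an inconsistency with 5.8.1.3 to be reconciled; it does not answer the concern.

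A reader might also infer that changes to the analysis could be aimed at one arm. Section 5.9.7 says otherwise: changes go to all data, involve the investigators and an outside biostatistician, and must be validated and justified. What remains is timing, since nothing requires a change to be fixed before results by arm are seen.

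That the manufacturer works with arms visible is inferred from silence on masking, although ExactVu images would reveal the platform. That it makes the 5.10.2 check with pathology to hand is not stated either. The pathology report enters through the site-visit comparison, which refers to the ultrasound system generally, and through 5.9.11.

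On size, the table's two columns are extremes. At a 33% detection rate, 12 outcome-neutral exclusions would all be csPCa-negative with probability 0.67¹² = 0.8%, and 30 with probability 0.67³⁰, about 6 in a million. The figures describe selective exclusion, not ordinary clerical error.

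Finally, 5.8.5.1 and 5.8.6 mention follow-up of inconsistent or unusual data, so queries are foreseen. But 5.9.11 still orders exclusion once an error is found, and no text says that a corrected record is kept.

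**Conclusion.** The concern holds in a limited form. As written, 5.9.11 produces avoidable post-randomisation exclusions in every arm, and the only comparison listed in 5.10.2 can add exclusions that by design arise only in the microUS-based arms. With no masking of data review specified, those exclusions may also be related to outcome.

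The bias could run either way. About 12 to 18 selectively removed csPCa-negative men would roughly double the false-positive risk, and similar numbers of csPCa-positive men would cost about 7 to 12 points of power. These sizes rest on assumed exclusion rates, on fully selective removal from one side, and on a normal approximation with 600 men per group. Outcome-neutral exclusion would be close to harmless. Nothing in the documents shows that selective exclusion is intended or likely; the point is that the rule permits it and need not.

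**What to change.** - **5.9.11:** resolve CRF errors and pathology/CRF inconsistencies by query against source and keep the randomised man in the primary analysis. Name the pathology report as the source for csPCa status. Report any remaining exclusions by arm and reason.
- **5.10.2:** base verification on a comparison that exists in every arm (CRF against pathology report), using listings that omit arm where feasible. The ExactVu image check may stay as a quality check but should not lead to exclusion.
- **5.9.7:** require any change to the algorithm to be fixed before results by arm are seen, and always report the analysis as prespecified alongside it.
- **Reconcile:** 5.8.1.6, which includes case data for all enrolled subjects, with 5.9.9 to 5.9.11, which exclude some; and the 5.8.5.1 demand for an ExactVu image for each subject with the conventional-ultrasound arm in 5.8.1.3.

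The cost is protocol and SAP wording, revised listings and some extra query work. No change to sample size is needed.

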5.10.4 Clinical quality assurance

This CIP identifies the elements of quality control principles that Exact Imaging applies to this clinical investigation, including the descriptions of procedures that ensure the clinical investigation is designed, conducted and monitored in accordance with applicable regulations and the requirements of the Ethics Board/IRB.

Exact Imaging maintains records to document the agreement of all parties involved in the investigation to the contents of this CIP.

5.11 Amendments to the CIP

All amendments to the CIP shall be agreed to between Exact Imaging and the study principal investigator and be recorded with a justification for the amendments. Deviations will be reviewed to determine the need to amend the CIP or to terminate the investigation.

When there are changes to the initial list of clinical investigators this list will not be formally updated by amendments at each change; Exact Imaging will maintain an updated list which will be available on request. The Ethics Board/IRB will be notified when required.

5.12 Deviations from the CIP

Investigators are not allowed to deviate from the CIP, except when the deviation is required to address the subject's rights, safety and well-being, or the scientific integrity of the clinical investigation. Any deviation from the CIP (this document) shall be recorded together with an explanation for the deviation. Deviations shall be reported to Exact Imaging, who is responsible for analyzing them and assessing their significance with regards to risk and safety. The CIP will be amended when the nature of the deviation requires it to be.

The reasons for withdrawal and discontinuation of any subject from the investigation shall be recorded.

Deviations will be recorded in the final report along with the justification for the deviation. Where applicable, the Ethics Board/IRB will be notified.

5.13 Device Accountability

All devices used in this study are cleared for clinical use in the appropriate jurisdictions and are being used for their cleared indications. The devices used in this study are not hazardous and do not need any special procedures, particular materials nor any special instructions for the safe return after the clinical investigation is completed.

5.14 Statements of Compliance

This clinical investigation shall be conducted in accordance with the ethical principles that have their origin in the Declaration of Helsinki.

This CIP and the investigation itself are designed to meet applicable requirements and regulations of the US FDA and other appropriate regulatory bodies for conducting clinical investigations.

The investigation will not begin until the required approval is obtained from the Ethics Board/IRB.

Any additional requirements imposed by the Ethics Board/IRB and/or the appropriate regulatory authority shall be followed

5.15 Informed Consent Process

This informed consent process is obtained by providing a potential study subject with an information sheet containing information about the purpose of the investigation, how to participate, benefits and risks, as well as information about the medical procedures to be performed. When a potential study subject signs the consent form, he agrees to enroll in the investigation. This clinical investigation does not involve emergency treatment where prior informed consent of the subject is not possible because of the subject's medical condition.

5.16 Adverse Events, Adverse device effects, and device deficiencies

5.16.1 Reporting adverse events

Unanticipated adverse device effects during clinical investigations of devices will be reported as appropriate to Exact Imaging, the Ethics Board/IRB and investigators participating in the study.

Exact Imaging will retain copies of adverse event reports as described in section 5.10.3.

5.16.1.1 Adverse event reporting process

Exact Imaging follows an internal company procedure, *Clinical Trial Incident Reporting Procedure*, to assess and report adverse events and other incidents associated with the investigation.

This process specified in this procedure is as follows:

1. An investigator will report any incident to Exact Imaging as soon as possible, and no later than 5 working days after first learning of the event.
2. Exact Imaging will conduct an evaluation of the incident, and determine the nature of the incident.
3. Exact Imaging will follow the process for reporting to the Ethics Board/IRB as required within the required timeframe, and in the required format.

5.16.1.2 Adverse event report format

Reports must follow the Ethics Board/IRB guidelines, and use the required reporting form.

5.16.1.3 Site Contacts

Site contact information is located on the individual site's approved Informed Consent Form (as per their ethics committee) and Clinical Trial Agreement

5.16.2 Device deficiency reporting process

If a device deficiency does not require immediate resolution, it will be discussed between the principal investigator, Study Monitor and Exact Imaging during the appropriate site visit, and resolved as described in section 5.8.5.1.

If a device deficiency required immediate resolution, the principal investigator will report the issue to the Study Monitor and Exact Imaging by phone. The Study Monitor will assess the issue, and work with Exact Imaging personnel to provide a solution or workaround in the necessary timeframe.

5.16.3 Foreseeable adverse events

There are no foreseeable adverse events or adverse device effects related to the use of ExactVu in this investigation.

5.17 Vulnerable population

Considerations for vulnerable populations such as minors are not required, as the inclusion criteria related to age excludes this population automatically.

Considerations for vulnerable populations such as those with potentially limited comprehension of research methods are not required, as enrolled subjects would undergo prostate biopsy regardless of whether or not they participate in the investigation.

Considerations for vulnerable populations such as those with language or cultural barriers are not required, as enrolled subjects would undergo prostate biopsy regardless of whether or not they participate in the investigation, and it is assumed they would have taken steps to comprehend the contents of the Patient Information and Consent form prior to signing it.

Considerations for vulnerable populations such as those that are socially or economically disadvantaged that participation in medical research is viewed as the only option to access otherwise unavailable medical treatment are not required, as enrolled subjects would undergo prostate biopsy regardless of whether or not they participate in the investigation.

5.18 Suspension or premature termination of the clinical investigation

If patients are harmed in any way this trial will be halted until the cause is identified and measures taken to correct it. The Ethics Board/IRB and any other affected regulatory body will be notified in accordance with section 5.16.

In the event that the investigation is terminated early, Exact Imaging will collect case report form data for consideration towards future clinical investigations. The Ethics Board/IRB shall be informed promptly and provided with the reason(s) for the termination.

5.19 Publication policy

Exact Imaging encourages the investigators to publish the results of this clinical investigation to reputable journals.

The conditions by which the results may be published are:

- Investigators are required to advise Exact Imaging of their intention to publish an article related to the results of the investigation.
- Exact Imaging requires the opportunity to review any articles pertaining to the results of the study prior to publication.
- All Site Principal Investigators and Study Principal Investigator must provide consent, in writing, prior to manuscript submission.

No subject will be identifiable in any published results.

